**Table 1. Allocation of LLINs**

| Type of LLIN | Targeted total number of LLINs for distribution | Number of clusters allocated |
|--------------|---|------------------------------|
| PPF LLIN     | 632,359   | 32                           |
| PBO LLIN     | 696,914   | 32                           |
| Total | 1,329,273                                | 64                    |

## 4 Delivery of the intervention

LLINs were distributed according to detailed national guidelines, which built on prior experience from a similar net distribution campaigns carried out in 2013-2014 and 2017-18, and incorporated guidance for LLIN distribution in the context of COVID-19, as well as lessons from food distribution during COVID-19. The overall goal of the 2020-21 LLIN distribution campaign was to reduce malaria morbidity and mortality in Uganda by achieving universal coverage with LLINs, aiming to ensure that: (1) 85% of the targeted population has access to a LLIN, and (2) 85% of LLINs distributed are utilised. Members of the research team engaged with Uganda's national committees that coordinated the LLIN universal coverage campaign, including the National Coordination Committee (NCC), which was responsible for overall coordination and oversight of campaign planning, implementation, and engagement with political and traditional authorities, the operations sub-committee, the logistics sub-committee and the advocacy, communication and social mobilisation sub-committee. All LLINs procured for the campaign were stored centrally in at the National Medical Stores warehouses in Entebbe and were distributed across the country in waves. The 32 districts selected for this study were included in Waves 3-5 and were scheduled to receive nets from November 2020 to March 2021. The research team worked closely with the NCC and other stakeholders to ensure that the nets were allocated per the randomisation scheme.

For each cluster we used a 'fried egg' approach for delivering the intervention ('egg white') and measuring our outcomes ('egg yolk'). The 'white' of the egg included one sub-county per cluster, where the MRC is located. PPF LLINs and PBO LLINs were distributed to the designated sub-county, as allocated in the

randomisation. The ‘yolk’ of the egg will be the target area directly surrounding each MRC, where care-seeking at the MRC is expected to be high (i.e. if someone within the target area develops malaria, they are likely to seek care at the MRC). To determine the population of the MRC target areas and to generate a sampling frame for the community surveys, the following were done: (1) define the target area of each MRC before the onset of the trial using data on village of residence from patients attending the MRCs, (2) map and enumerate all households within the MRC target areas before the 12-month community survey, (3) conduct a census survey within each MRC target area to generate an accurate estimate of the study population in which study outcomes will be measured concurrently with the 12-month community survey.

## 5 Evaluation procedures

---

### 5.1 Enumeration surveys

To estimate the population of the MRC target areas, and to generate a sampling frame for the cross-sectional community surveys, we will enumerate and map all households within each target area prior to the evaluation. In advance of the enumeration surveys, investigators will meet with local officials and community representatives to discuss the study and plans for the household enumeration. Using a map of the boundaries of the MRC target areas, project personnel will systematically cover the entire area within the boundaries to identify and enumerate all households. A household will be defined as any single permanent or semi-permanent dwelling structure acting as the primary residence for a person or group of people that generally cook and eat together. Some households may include members who sleep in other dwelling structures within the same compound, if the members are still dependent on the head of household in the main household. All households identified will be assigned sequential unique IDs. Household locations will be mapped using GPS receivers. Readings will be taken from the door of the household, if possible, or from a point that is most representative of the household. At each household, a reading will be taken every five seconds for 2 minutes, and the average values from these readings will be recorded (Easting, Northing, and Altitude) in UTM units. Only GPS coordinates will be picked from the households. No additional data will be collected during the enumeration survey.

### 5.2 Health facility-based surveillance

At each MRC (Appendix A), individual-level data from standardised registers for all patients presenting to the outpatient departments are entered into an Access database by on-site data entry officers. Primary data captured comes from the HMIS 002 standardised form (Appendix C) and includes location of residence (parish and village), age, gender, body temperature, history of subjective fever, type of malaria test done (rapid diagnostic test or microscopy), malaria diagnostic test results, any diagnoses given, and any treatments prescribed. Data from each MRC will be submitted to the team in Kampala on a monthly basis using a secure on-line system. Standardised data checks will be applied to assess for missing data and data errors. Data queries will be submitted back to the sites and corrected whenever possible. Interval data submitted from the MRCs will be merged into an existing master database. Each time the master database is updated, existing programmes will be run to perform variable transformations and generate standardised indicator variables.

## 5.3 Community surveys

Cross-sectional community surveys will be conducted 12 and 24 months after nets are distributed. The surveys will include two components: (1) a household survey targeting heads of households, and (2) a clinical survey of children aged 2-10 years.

### 5.3.1 Sampling frame

The sampling frame for the community surveys will be generated from the enumeration of the MRC target areas (which will be conducted prior to the onset of the evaluation). Households will be randomly selected from each of the 64 clusters and screened until 50 households with at least one child aged 2-10 years are enrolled (at least 3,200 households). If an enrolled household has no children of appropriate age, they will be included in the household survey only, and will not take part in the clinical survey.

### 5.3.2 Definitions

**Household:** A household will be defined as any single permanent or semi-permanent dwelling structure acting as the primary residence for a person or group of people that generally cook and eat together. Some households may include members who sleep in other dwelling structures within the same compound, if the members are still dependent on the head of household in the main household.

**Head of household:** The head of household is an adult person or persons who primarily make decisions for the general household (e.g. decisions on healthcare, income, etc.), including emancipated minors.

**Household resident:** A resident within each household will be defined as a person who intends to have a sleeping place primarily at that location for a period of the next 6 months. This may include people who sleep in a separate house within the same compound, if they are still dependent on the head of household for decisions on finances and health care.

### 5.3.3 Household selection criteria

The inclusion criteria for household participation in the community surveys are: (1) at least one adult aged 18 years or older present; (2) adult is a usual resident who slept in the sampled household on the night before the survey; (3) agreement of the adult resident to provide informed consent for the household survey. The exclusion criteria are: (1) dwelling destroyed or not found; (2) household vacant; (3) no adult resident home on more than 3 occasions.

### 5.3.4 Household questionnaire

The household questionnaire will be administered to the head of the household (or their designate), after obtaining their consent using a hand-held tablet computer. Information will be gathered on the characteristics of households and residents, proxy indicators of wealth including ownership of assets, and ownership and use of LLINs in the households, specifically focusing the nets distributed in the LLIN campaign. The household survey questionnaire has been adapted from prior cross-sectional community surveys conducted in Uganda, including the national Malaria Indicator Survey [24-27].

### 5.3.5 Clinical survey recruitment

All children aged 2-10 years from enrolled households who are present will be eligible for participation in the clinical survey. Children will be identified from the household survey questionnaires.

### **5.3.6 Clinical survey selection criteria**

The inclusion criteria are: (1) child aged 2-10 years; (2) usual resident who was present in the sampled household on the night before the survey; (3) agreement of parent/guardian to provide informed consent; (4) agreement of child aged 8 years or older to provide assent. The exclusion criterion is: (1) child not home on day of survey.

### **5.3.7 Clinical survey procedures**

The clinical surveys will include measurement of temperature, subjective fever and a finger-prick blood sample for measurement of thick blood smear and haemoglobin (in children < 5 years), and filter paper blood sample.

## **5.4 Economic evaluation**

An economic evaluation will be conducted to compare the incremental costs and cost-effectiveness of LLIN strategies using either Royal Guard LLINs or PBO LLINs in accordance with the reference case for economic evaluations in low- and middle-income countries [28]. The analysis will combine primary data on costs and effectiveness from the trial with additional secondary data to inform policy choices regarding the choice of LLIN. Efficiency will be measured in incremental cost-effectiveness ratios. A decision tree will be used to calculate the incremental cost-effectiveness of the Royal Guard LLIN compared to PBO LLINs [29, 30].

# **6 Sample size calculations**

---

## **6.1 Primary outcome**

Our sample size of 32 clusters per arm was calculated to detect a 26% decrease (incidence rate ratio (IRR) = 0.74) in the incidence of malaria over the 24 month period following the intervention (the primary endpoint of the study) between the two study arms, given a power of 80% and a two-sided significance level of 0.05. This sample size calculation assumes an incidence of 332 malaria cases per 1000 person-years in the control arm and a coefficient of variation (CV) of 0.42 calculated from the 14 MRCs where estimates of malaria incidence are available over the last 6 month at the time of protocol development.

## **6.2 Secondary outcomes**

We will sample all eligible children aged 2-10 years from 50 households in the 64 clusters in each round of surveys, aiming to maximise the potential prevalence ratio detectable in the intervention arm, as well as the cost/value of the trial. Assuming an average of 1.8 children aged 2-10 years per household, we estimate that we will survey 5,760 children from 3,200 households. Assuming a coefficient of variation of 0.4, across a wide range of prevalence measures in the control arm (10-70%) our sample size will allow us to detect a 25-28% decrease in the prevalence measure of interest (prevalence ratio (PR) = 0.72-0.75), given a power of 80% and a two-sided significance level of 0.05.

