In 2017, we also conducted a clinical survey of parasite prevalence in children aged 2-10 years [17]. In total, 5,196 households and 8,834 children with blood smear results were included in the analyses. Overall, parasite prevalence was 26.0%, ranging from 8.0% in the South West to 53.1% in East Central. Limiting the analysis to children 2-4 years of age residing in the five regions, parasite prevalence was 21.4%. Comparisons made between the 2009 and 2014-15 Malaria Indicator Surveys and the 2017 survey (Figure

[figure not shown]

Figure 1. LLIN ownership and coverage from 2014 to 2017
Reduced ownership & coverage 3 years after the LLIN distribution campaign.

[figure not shown]

Figure 2. Change in parasitaemia over time. Parasitaemia in children 2-4 years fell from 46% in 2009 to 17% in 2014, but rose to 21% in 2017.

2) indicated that parasite prevalence fell from 45.6% to 16.9% between 2009 and 2014-15, with significant decreases in all five regions of the country ($p<0.001$ for all comparisons). However, in 2017, prevalence increased in all areas, which was statistically significant in the Mid-Eastern (6.0% vs. 19.1%, $p<0.001$) and Mid-Western regions (19.5% vs. 25.7%, $p=0.02$).

Thus, although the 2013-14 national LLIN distribution campaign successfully reached its target coverage level, we observed a limited effect on clinical malaria indicators and transient reduction in parasite prevalence. Moreover, LLIN coverage dropped substantially after 3 years. These findings highlight the challenges of relying on LLINs as the primary method of vector control in Uganda.

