### **1.3 Study site**

The NMCD and supporting partners will distribute LLINs nationwide across Uganda, including the 32 districts included in this study. Districts were selected to participate in the study based on the following criteria: (1) Not receiving IRS, (2) Selected by the NMCD to receive PBO LLINs, based on available insecticide resistance data and guided by Uganda's insecticide resistance management plan [23], (3) high malaria transmission intensity. Once the districts were identified, we then selected MRCs to bring the total to 64.

The selection criteria for the LLINEUP2 MRC sites, included: (1) Level III/IV high-volume, public health facility (HC III or HC IV), (2) Total OPD attendance between 1000-2000 patients per month, (3) Evidence of weekly and monthly reporting in DHIS2, (4) Presence of a functional laboratory at the facility. In addition, we aimed to ensure that MRCs within the same district were comparable in terms of level-of-care and were located in different sub-counties to avoid contamination.

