## 8.2 Secondary outcomes from cross-sectional surveys

Secondary outcomes from the 12 and 24 month cross-sectional surveys will include the following:

1. Prevalence of parasitemia in children 2-10 years of age - defined as the proportion of children with a positive thick blood smear by microscopy.
2. Prevalence of anemia in children 2-4 years of age - defined as the proportion of children with a hemoglobin level < 11 g/dL.
3. Measures of LLIN ownership, coverage and use defined as follows:
  - a. LLIN ownership - the proportion of households that owned at least one LLIN),
  - b. Adequate LLIN coverage - the proportion of households that owned at least one LLIN for every two residents.
  - c. LLIN access - proportion of residents who could sleep under a LLIN, if each LLIN in the household were used by up to two residents
  - d. LLIN use - the proportion of household residents who reported sleeping under an LLIN the previous night.

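### The survey power statement (25-28% decrease detectable over 10-70% prevalence) holds only from about 20% prevalence upward; at 10% the figure is about 32%, and anaemia has no calculation of its own

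*SAP*

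**What the plan says.** SAP 6.2 gives one power statement for the prevalence outcomes of the community surveys. All eligible children aged 2-10 are sampled "from 50 households in the 64 clusters in each round of surveys". The yield is then set out: "Assuming an average of 1.8 children aged 2-10 years per household, we estimate that we will survey 5,760 children from 3,200 households". With a coefficient of variation of 0.4, the section concludes that "across a wide range of prevalence measures in the control arm (10-70%) our sample size will allow us to detect a 25-28% decrease", equivalent to prevalence ratios of 0.72-0.75, "given a power of 80% and a two-sided significance level of 0.05". Protocol 13.4.2 makes the same statement. Neither document names the formula.

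The number of clusters comes from SAP 6.1: "Our sample size of 32 clusters per arm was calculated to detect a 26% decrease" in the primary outcome.

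The statement is worded for whichever prevalence measure is of interest. SAP 8.2 lists several such measures, among them "Prevalence of anemia in children 2-4 years of age". No number of children aged 2-4, no anaemia prevalence and no detectable difference for anaemia appears in either document.

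**The concern.** In a cluster trial with a fixed coefficient of variation, the detectable relative decrease grows as prevalence falls, because binomial sampling error becomes large relative to the prevalence itself. A spread of only three percentage points (25% to 28%) over a sevenfold range of prevalence looked too narrow for 90 children per cluster.

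If the low end is wrong, a null result at low prevalence would be read against 80% power that the design does not have. The same would happen with anaemia if a reader applied a figure built on ages 2-10 to an outcome measured only at ages 2-4.

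The documents do not fix the control prevalence expected in these districts. The 2017 survey reported: "Overall, parasite prevalence was 26.0%, ranging from 8.0% in the South West to 53.1% in East Central". The present districts were selected for "high malaria transmission intensity", which points upward. Against that, the control net here is a PBO net, and in the sponsor's earlier Ugandan trial (Protocol 1.8, SAP 1.1) the PBO arm had prevalences of 10.7%, 10.6%, 11.8% and 17.1% at 6, 12, 18 and 25 months.

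**Working it through.** **Inputs**

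- Clusters per arm: c = 32 (SAP 6.1).
- Children per cluster per survey: m = 50 × 1.8 = 90; check 5,760 / 64 = 90 (SAP 6.2). The 12- and 24-month surveys are analysed separately (SAP 8.2.1), so 90 is the number for each analysis.
- Coefficient of variation: k = 0.4 (SAP 6.2).
- 80% power, two-sided 5%: (1.960 + 0.842)² = 7.849.

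**Formula** (standard CV-based formula for proportions, unmatched clusters), with p1 = PR × p0:

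c = a + 7.849 × [p0(1−p0)/m + p1(1−p1)/m + k²(p0² + p1²)] / (p0 − p1)²

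Here a = 1 is the usual added cluster and a = 0 omits it. The documents do not say which was used, so both are shown. Power is Φ( √{(32 − a)(p0 − p1)² / [...]} − 1.960 ), where [...] is the bracket above.

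**Step 1: the plan's figure at the top of the range.** At p0 = 0.70 the detectable decrease is 25.2% (a = 0) or 25.6% (a = 1). The stated 25% is reproduced without the added cluster, so the formula fits the plan's number there.

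**Step 2: the bottom of the range.** At p0 = 0.10 and PR = 0.72, p1 = 0.072:

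- control sampling term: 0.09/90 = 0.001000
- intervention sampling term: 0.072 × 0.928/90 = 0.000742
- between-cluster term: 0.16 × (0.01 + 0.005184) = 0.002429
- sum 0.004172; squared difference 0.028² = 0.000784
- c = a + 7.849 × 0.004172/0.000784 = a + 41.8

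The plan has 32 clusters per arm. A 28% decrease at 10% prevalence would need 42 (a = 0) or 43 (a = 1).

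**Step 3: the whole range** (m = 90, c = 32, k = 0.4)

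| Control prevalence | Detectable decrease, a = 1 / a = 0 | Power for PR 0.72, a = 1 / a = 0 |
|---|---|---|
| 10% | 32.0% / 31.5% | 67.5% / 68.9% |
| 15% | 29.7% / 29.3% | 74.6% / 75.9% |
| 20% | 28.5% / 28.1% | 78.5% / 79.8% |
| 26% | 27.6% / 27.2% | 81.3% / 82.5% |
| 50% | 26.1% / 25.7% | 85.8% / 86.9% |
| 70% | 25.6% / 25.2% | 87.2% / 88.2% |

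The detectable decrease equals 28.0% at a prevalence of 22.9% (a = 1) or 20.4% (a = 0).

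**Step 4: could another reading give 28% at 10%?**

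- Other two-sided variants (t quantiles, log-ratio scale, design effect with the implied intracluster correlation) give 31.2-32.8% at 10%. A constant between-cluster standard deviation gives about 35%.
- A one-sided test gives 28.8% at 10% but 23.0% at 70%, and it contradicts the stated two-sided level.
- With 32 clusters per arm, 28% at 10% would need about 235 (a = 1) or 204 (a = 0) children per cluster, or a coefficient of variation of 0.30 (a = 1) or 0.31 (a = 0).
- With 180 children per cluster and a = 0 the range is 28.4% to 25.0%, close to the stated one. That would mean 5,760 children per arm or two pooled rounds, and the documents provide for neither.
- The survey model in SAP 8.2.1 has random effects for cluster and household only. It has no district term or baseline covariate that would gain precision.

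**Step 5: anaemia (illustration only).** Assume 30 children aged 2-4 per cluster, that is three of the nine age-years from 2 to 10, with 20 and 40 as a range. With a = 1 and k = 0.4, the detectable decrease is:

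| Anaemia prevalence | 20 children | 30 children | 40 children |
|---|---|---|---|
| 10% | 48% | 42% | 39% |
| 20% | 38% | 34% | 32% |
| 30% | 33% | 31% | 29-30% |
| 50% | 29% | 28% | 27% |
| 70% | 27% | 26-27% | 26% |

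**The case against.** The strongest reply is about weight. The gap is some four percentage points at one end of a range, in a secondary-outcome statement on which no analysis rule depends. It is of the same order as the uncertainty in the assumed coefficient of variation: moving that from 0.40 to 0.45 shifts the figure at 20% prevalence from 28.5% to 30.9% (a = 1). At the 26.0% found in 2017 the stated range holds, and these districts were chosen for high transmission. The earlier trial's lower figures come from other clusters in Eastern and Western Uganda. All of this stands, and it keeps the point modest. It does not make the sentence correct, because the plan itself chose 10% as the lower bound of its claim.

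On anaemia, it is fair to say that no anaemia figure is wrong, since none is given, and that at 50% prevalence 30-40 children per cluster would put it at 27-28%. The gap is one of missing detail. Even so, a sentence worded for any prevalence measure will be read as covering anaemia, and fewer children per cluster can only raise the detectable decrease. The net measures also have denominators other than children aged 2-10; stating which outcome the figure covers would settle that too.

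Finally, the 20% threshold is approximate. It depends on the added cluster, and the formula ignores correlation between children in one household. Allowing for that correlation would only widen the gap.

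**Conclusion.** The statement is wrong as written for control prevalence between 10% and about 20%. At 10% the stated inputs give a detectable decrease of 31.5-32.0%, and power of 67-69% for a prevalence ratio of 0.72. From about 20% upward (about 23% with the added cluster) the parasitaemia figure is right, subject to rounding at the 70% end. This rests on the documents' own inputs and on the standard CV-based formula, which reproduces the upper part of the range; other plausible two-sided methods give a similar result at 10%. For anaemia the documents give no basis for any figure. The sizes shown depend on an assumed 20-40 children aged 2-4 per cluster, and only the direction is certain. The primary outcome calculation is not affected.

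**What to change.** In SAP 6.2 and Protocol 13.4.2:

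1. Either restate the parasitaemia figure as a decrease of about 25-32% (prevalence ratio about 0.68-0.75) over control prevalence 10-70%, or keep 25-28% and limit it to control prevalence of about 20-70%. If the formula includes the added cluster, the lower limit becomes about 23% and the 70% end rounds to 26%.
2. Name the formula and say whether it includes the added cluster.
3. State that the figure applies to parasitaemia at ages 2-10 and not to anaemia. Add a line for anaemia with the expected number of children aged 2-4 per cluster, the assumed prevalence range, the coefficient of variation and the resulting detectable decrease.

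The cost is text only, one paragraph in each document, with no change to sample or analysis. The price is a less favourable claim below about 20% prevalence.
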